## 3.3. Exploratory Endpoint(s)

Protocol specified exploratory efficacy endpoints include:

- Proportion of participants achieving resolution of target ulcer(s) by Week 24
- Time (in days) to resolution of target ulcer(s) up to Week 24
- Change from baseline in total surface area of target ulcer(s) over time up to Week
   24
- Correlation between change in Hb and target ulcer(s) healing at Weeks 12 and 24
   Healing at Week 12 and 24 is defined as achieving confirmed re-epithelialization by Week 12 and Week 24 which is defined as participants achieving resolution of the target ulcer(s),

- Correlation between change in hemolytic parameter (% reticulocytes, indirect bilirubin, LDH) and target ulcer(s) healing at Weeks 12 and 24
- Change from baseline in PRO HRQOL measures: PROMIS-37 v2.0 Pediatric Profile/PROMIS-43 v2.1 at Weeks 12 and 24
- Change from baseline in pain level linked to target ulcer(s) assessed by VAS at Weeks 12 and 24
- PGI-C score at Weeks 12 and 24
  - PGI-C questionnaire includes 7 responses which are 1) very much improved, 2) much improved, 3) minimal improved, 4) no change, 5) minimal worse, 6) much worse and 7) very much worse.
- CGI-C score at Weeks 12 and 24

CGI-C questionnaire includes 7 responses which are 1) very much improved, 2) much improved, 3) minimal improved, 4) no change, 5) minimal worse, 6) much worse and 7) very much worse.

#### 3.4. Baseline Variables

#### Randomized Treatment Period:

- Voxelotor: Baseline period is defined as Day 1 of the study.
- Placebo: Baseline period is defined as Day 1 of the study.

## Open-Label Treatment Period:

- Voxelotor: Baseline period is defined as Day 1 of the study.
- Delayed voxelotor: Baseline period is defined as Day 1 of the study.

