Visit Number (Week)	Visit 1 (Week -6 to - 2)	Visit 2 (Week -2)	Visit 3 (Week 0)	Visits 4-8 b (Week 2-10)	Visit 9 (Week 12)	Visit 10-14° (Week 14- 22)	Visit 15 (Week 24)	Visit 16-A & onward d (Week 28)	Visit 16-B (Week 28)	
Visit Day	-42 to -14	-14	Day 1	Day 14-70	Day 84	Day 96-154	Day 168	Day 196 & onward	Day 196	
Visit Window	_	+3 days	+1 day	±3 days	±3 days	±3 days	±3 days	±5 days	±7 days	_

- t. Study drug will be dispensed at the Day 1, Week 6, Week 12, and Week 18 visits. For participants who continue to receive voxelotor beyond 12 weeks in the Open-label Treatment Period (See Section 5.1), study drug will be dispensed every 12 weeks.
- Participants demonstrating initial ulcer-re-epithelization at Week 12 will continue treatment in their assigned treatment group for an additional 2 weeks to confirm ulcer resolution.
- v. Participants transitioning to a program providing voxelotor through an alternative source will complete assessments on the day they transition to that program. Study drug for this study should not be taken on the day of that visit (dose will be taken on that day as part of the alternative source program).
- w. Only required for participants transitioning to a program providing voxelotor through an alternative source

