## 2.3.2. Treatment Group and Reporting Period for Analysis

In the study schematic in Figure 1. Study Schema, the study period and treatment groups to be included in the primary and open-label analysis.

Efficacy and Safety: Primary analysis (Randomized Treatment Period):

- Treatment groups:
  - Voxelotor: participants randomized to voxelotor.
  - Placebo: participants randomized to placebo.
- Reporting Period:
  - From Day 1 through Week 12 for subjects who either do not achieve confirmed reepithelialization or achieve it before or at Week 12 visit.
  - From Day 1 through Week 14 for subjects who have the initial skin reepithelialization confirmed at Week 12 and then the 14-week visit will be used to confirm resolution.

Day 1 is defined as the date of randomization. The last day (i.e. Week 12 visit or Week 14) of randomized treatment period is defined as the last day entered on the disposition page for end of randomized treatment period.

Efficacy: Open-label analysis (Open-Label Treatment Period):

- Treatment groups:
  - Voxelotor: participants randomized to voxelotor who received at least one dose of voxelotor.

- Delayed voxelotor: participants randomized to placebo during Randomized Treatment Period (through Week 12) and who received at least one dose of voxelotor on or after the Week 12 visit.
- Total: participants who received at least one dose of voxelotor.

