## Reporting Period:

- After Week 12 (one day after Week 12 visit) through Week 24 for subjects who either
  do not achieve confirmed re-epithelialization or achieved it before or at Week 12
  visit.
- After Week 14 (one day after Week 14 visit) through Week 24 for subjects who have the initial skin re-epithelialization confirmed at Week 12 and then the 14-week visit will be used to confirm resolution.

Safety: Open-label analysis (Open-Label Treatment Extension Period which is combining the entire Open-Label Treatment Period and the Follow-up Period):

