#### Baseline Value

Baseline for all assessments other than laboratory or vital sign parameters, will be defined as the last available pre-treatment value taken on or before the day of randomization and will be used for summary of baseline characteristics and change from baseline analyses, as appropriate.

Baseline for a given laboratory parameter will be defined as the average of all non-missing laboratory values on or prior to the randomization Date.

Baseline for a given vital sign parameter will be defined as the average of all non-missing vital sign value on or prior to randomization Date.

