#### Change from Baseline

Change from baseline for a given endpoint is defined as the Study Day value minus the Baseline value.

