#### 6.6.2. Laboratory Data

All hematology and chemistry laboratory assessments were performed by a central laboratory. Laboratory data will be converted into SI for the analysis. The protocol-specified clinical laboratory (Table 2) findings will be summarized using descriptive statistics by treatment group, without any imputation.

Descriptive statistics will be presented for baseline, each evaluation post baseline, and change from baseline for each post baseline evaluation through 28 days after last dose date.

Laboratory abnormalities will be graded via the Common Terminology Criteria for Adverse Event (CTCAE) or protocol defined severity classification. Laboratory abnormality shifts from baseline will be summarized by treatment group and by reporting periods.

To assess liver injury, a listing of the participants potentially meeting Hy's Law criteria and E-DISH plots will be produced.

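### Open-label laboratory shifts for the Delayed voxelotor group are measured from a Day 1, pre-placebo baseline, so placebo-phase changes are credited to, or hide changes in, the voxelotor period

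*SAP*

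**What the plan says.** **Baseline.** For the open-label period SAP 3.4 states: "Delayed voxelotor: Baseline period is defined as Day 1 of the study". SAP 2.3.3 is consistent with this. A laboratory baseline is the "average of all non-missing laboratory values on or prior to the randomization Date", vital signs are averaged in the same way, and every other assessment uses the "last available pre-treatment value taken on or before the day of randomization". The change rule is general: "Change from baseline for a given endpoint is defined as the Study Day value minus the Baseline value". No section defines a further baseline at the start of open-label voxelotor.

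**Who is in the group, and when.** For open-label efficacy, SAP 2.3.2 describes Delayed voxelotor as "participants randomized to placebo during Randomized Treatment Period (through Week 12) and who received at least one dose of voxelotor" from the Week 12 visit on; its safety definition is similar. The open-label efficacy period runs "After Week 12 (one day after Week 12 visit) through Week 24 for subjects who either" have no confirmed re-epithelialization or reached it by the Week 12 visit. For those whose first re-epithelialization is seen at Week 12, it starts after the Week 14 visit. The safety period starts at the same points and runs to the end of the study. The later start matches a footnote to the schedule in Protocol Appendix 1: "Participants demonstrating initial ulcer-re-epithelization at Week 12 will continue treatment in their assigned treatment group for an additional 2 weeks to confirm ulcer resolution".

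**Output.** SAP 6.6.2 states: "Laboratory abnormality shifts from baseline will be summarized by treatment group and by reporting periods". SAP 2.3.2 also defines a Total group of everyone who received voxelotor.

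**The concern.** The reporting periods separate time on placebo from time on voxelotor for the switchers, but the reference value does not follow. Day 1 is the pre-voxelotor value for the Voxelotor group and the pre-placebo value for the Delayed group. In an open-label shift table the two columns therefore show different contrasts under one label, and a Total column pools them.

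This matters mainly for safety. SAP 2 records that the sponsor paused dosing because of the overall number of deaths and then terminated the study, so readers of the final report will look closely at laboratory findings by period. For the switchers, such a reader needs to know which abnormalities were already present when voxelotor began. A Day 1 shift table does not show that.

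**Working it through.** There is no stated figure to reproduce; the point follows from the definitions.

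**1. What the change formula contains.** For a Delayed voxelotor participant:

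Week 24 − Day 1 = (Week 12 − Day 1, on placebo) + (Week 24 − Week 12, on voxelotor).

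The scheduled days are 1, 84 and 168 (SAP Appendix 2.1). The placebo part spans 84 − 1 = 83 of the 168 − 1 = 167 days, about 50%, and more for those who switch at Week 14.

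**2. What that does to a shift table.** Hypothetical grades for one participant:

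| Pattern | Day 1 | Week 12 (placebo) | Week 24 (voxelotor) | Open-label shift from Day 1 | Open-label shift from last pre-voxelotor value |
|---|---|---|---|---|---|
| A | 0 | 2 | 2 | 0 to 2 | none |
| B | 1 | 0 | 1 | none | 0 to 1 |
| C | 0 | 1 | 2 | 0 to 2 | 1 to 2 |
| D | 0 | 0 | 1 | 0 to 1 | 0 to 1 |

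Pattern A puts a placebo-phase shift into the voxelotor period. Pattern B hides a voxelotor-phase shift. Pattern C overstates the size of one. Only pattern D is the same under both baselines.

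**3. Size in the upward direction.** Let *a* be the proportion who develop a shift on placebo that persists, and *b* the proportion with a new shift on voxelotor. With independence and full persistence,

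reported open-label proportion = 1 − (1 − *a*)(1 − *b*).

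With *b* = 10% (assumed):

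| *a* (assumed) | Calculation | Reported | Excess over 10% | Excess participants if 40 switch |
|---|---|---|---|---|
| 5% | 1 − 0.95 × 0.90 | 14.5% | 4.5 points | 1.8 |
| 10% | 1 − 0.90 × 0.90 | 19% | 9 points | 3.6 |
| 15% | 1 − 0.85 × 0.90 | 23.5% | 13.5 points | 5.4 |

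Forty is the planned arm size, so the last column assumes that every planned placebo participant switches. If half of a Total column were Delayed participants (assumed), its excess would be half as large: 2.25, 4.5 or 6.75 points.

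**4. Size in the downward direction.** Each pattern B participant is a voxelotor-period shift that the table does not count. The documents give no rates from which to net the two directions.

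**5. Can the reader undo it?** For mean changes, roughly: subtract the Week 12 mean from the Week 24 mean, provided the same participants contribute. For a shift table, no, because each person's grade at the switch is not in it.

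**The case against.** The strongest reply is that Day 1 is a proper baseline and that little depends on it. Much of this stands.

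- **Ulcer area.** A reader might infer that the Week 24 ulcer-area change is also wrongly baselined. The documents do not support that. Protocol 8.3 sets the ulcer baseline at Day 1, and the exploratory endpoint is a cumulative change over time to Week 24, summarised descriptively. Day 1 suits that quantity in both groups. Re-baselining only one column would set unlike changes side by side, and ulcers already closed at the switch could shrink no further.
- **Direction.** A reader might infer that open-label shifts are simply inflated. Pattern B shows that they can also be understated.
- **Uniqueness.** A reader might infer that only the Delayed group has before-and-after voxelotor data. The Voxelotor group also has Screening and Day 1 values before drug. What distinguishes the Delayed group is a placebo phase followed by voxelotor in the same person.
- **Purpose.** SAP 6.6.2 does not say that splitting by period is meant to isolate drug effects. The point needs no such purpose: whatever the intent, the table's period label and its reference value do not match for the switchers.
- **Vital signs.** SAP 6.6.3 does not say that these are split by reporting period, so the point reaches them only if they are.

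None of this answers the laboratory shift tables, where the period is open-label, the baseline precedes placebo, and no other section corrects it.

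**Conclusion.** The point holds for open-label laboratory shift and change summaries in the Delayed voxelotor group, and for any Total column that includes it. The mismatch itself follows from the SAP's definitions and needs no assumption. Its size does: the reported 14.5% to 23.5% against 10% rests on assumed rates, independence and full persistence, and shows the upward direction only. The error is zero only if nothing changed on placebo, or if opposite errors happen to cancel.

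The Week 12 primary and secondary comparisons are untouched, because Day 1 is the right baseline for both arms there. The SAP also does not depart from the protocol on the ulcer baseline. This is a low-severity point, worth acting on because the affected tables concern safety and the correction is cheap.

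**What to change.** For Delayed voxelotor, define an additional open-label baseline: the last non-missing value on or before the first open-label voxelotor dose. Use it for open-label laboratory shifts and changes, and for vital signs if they are summarised by period.

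Set it by dose date, not by windowed visit, for three reasons:

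- Some participants stay on placebo until Week 14.
- The laboratory Week 12 analysis window runs from Day 2 to Day 125, which is 125 − 84 = 41 days past the target day, and could pick up values taken on voxelotor.
- An inadequate Week 12 blood sample may be redrawn within 7 days (Protocol 6.10), possibly after the first open-label dose. Where that leaves Day 1 as the last pre-dose laboratory value, flag the participant.

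Keep Day 1 for the cumulative ulcer-area trajectory to Week 24. A change since the switch may be added as a labelled supplement.

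The cost is one extra baseline flag and clear labels, since hematology, chemistry and vital signs are already scheduled at Week 12. There are two drawbacks. One group carries two baselines, and the new laboratory baseline is a single value, noisier than the pre-randomisation average and computed differently from the Voxelotor column. SAP version 4 postdates the last participant visit, so the report should state that these summaries were added.

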#### 3.4.1. Stratification Variable

## Stratification factors (variables) are defined as followed:

 Ulcer size: total target ulcer surface area (ie, sum of all target ulcer surface areas) at baseline visit (Day 1).

CCI

 Duration of ulcer(s): longest duration of any individual target ulcer(s) present at baseline visit (Day 1).

CC

CCI

Note that the stratification variables will be derived based on the baseline visit (Day 1) in the clinical database. If the derived stratification variables are not matched with IRT stratified randomization factors, the derived stratification variables from clinical database will be used for the analysis. If duration of ulcer(s) or ulcer size not are available in the clinical database, the data from IRT will be used for the analysis.

#### 3.4.2. Other Baseline Variables to be Summarized

- Demographic characteristics include gender, race, ethnicity, geographical region, country, site, and age at Screening visit.
- Baseline disease characteristics (including number of target leg ulcer(s), total surface area
  of target leg ulcer(s), and maximum duration of target leg ulcer(s))

- Physical examination at Screening include height (cm), weight (kg) and BMI (kg/m²)=weight (kg)/[height (m)]²
- Sickle cell disease genotype
- Hydroxyurea use

## 3.5. Safety Endpoints

#### 3.5.1. Adverse Events

MedDRA will be used to code all AEs (non-serious and serious) with respect to system organ class and preferred term (PT) using most current version of the MedDRA dictionary.

TEAE is defined as an AE that occurs or worsens during the on-treatment period as defined in Section 2.3.3.

## 3.5.2. Laboratory Data

The following safety laboratory tests (Table 2) will be collected. Analyses for banked biospecimens are out of scope for this SAP.

Table 2. Protocol-Required Safety Laboratory Assessments			
Hematology	Serum Chemistry		
RBCs	• ALT		
Hematocrit	Albumin		
Hemoglobin	Alkaline phosphatase (ALP)		
Platelet	AST		
White blood cells with differential (basophils,	Bicarbonate		
eosinophils, neutrophils, monocytes, and lymphocytes)	Blood urea nitrogen		
% and absolute reticulocytes	Chloride		
RBC distribution width	Calcium		
Mean corpuscular volume	Creatinine		
Mean corpuscular hemoglobin concentration	Glucose		
HbSS, HbS/β0 thalassemia test (at Screening only	• LDH		
for medical diagnosis of SCD, if diagnosis is not	Sodium		
documented in medical chart)	Potassium		
	Bilirubin (total, direct, and indirect)		
	Total proteins		
	Phosphorus		

## 3.5.3. Other Safety Endpoints

- Complete physical examination and brief physical examination: if any finding on the
  physical examination is considered by the investigator to be 'clinically significant',
  the event is to be recorded as medical history or an AE, as appropriate.
- Vital Signs: vital sign parameters include blood pressure, heart rate, and temperature.

## 4. ANALYSIS SETS (POPULATIONS FOR ANALYSIS)

For purposes of analysis, two main analysis populations are defined for this study as below.

Population	Description
	All randomized participants according to the treatment group to
_	which they were randomized, regardless of the treatment received
	All randomized participants who received at least one dose of study drug, regardless of the group to which they were randomized

#### 5. GENERAL METHODOLOGY AND CONVENTIONS

#### 5.1. Hypotheses and Decision Rules

The hypothesis testing for the primary endpoint is to compare the proportion of participants achieving resolution of the target ulcer(s) by Week 12 in voxelotor vs. placebo group as follows:

$$H_0$$
:  $p_v=p_c$  vs.  $H_1$ :  $p_v\neq p_c$ ,

where pv and pe are the proportion of participants achieving resolution of the target ulcer(s) by Week 12 in voxelotor and placebo group, respectively.

## 5.2. General Methods

#### 5.2.1. Analyses for Binary Endpoints

The exact CMH general association test will be used for binary endpoints. The estimated proportions with 95% CI by treatment group, the estimated proportion difference (voxelotor vs. placebo) with 95% CI and the p-value will be provided.

Descriptive statistics including the number of participants (N) and percentage (%) will be provided by treatment group.

## 5.2.2. Analyses for Continuous Endpoints

## 5.2.2.1. Mixed Model Repeated Measures (MMRM)

The MMRM model will be used for the specific endpoint and will include fixed effects terms for:

- Treatment group (as a categorical variable);
- Scheduled visit time point (as an ordered categorical variable);

PFIZER CONFIDENTIAL TMF Doc ID: 98.03 Page 21 of 43 Interaction between treatment group and scheduled visit time point.

The restricted maximum likelihood (REML) estimation method will be used with an unstructured covariance matrix to describe the correlation among different visits from the same participant. If there are convergence issues with the model, the following structures will be considered in the order listed below until convergence is obtained:

- Spatial Power (SP);
- Autoregressive-1 (AR(1));
- Compound Symmetry (CS).

The Kenward-Roger degrees of freedom will be used.

The model adjusted estimates for the endpoint for each treatment group at each specified time point will be provided using the least squares (LS) means and their 95% confidence intervals (CIs).

Descriptive statistics including the number of participants (N), mean, standard deviation (SD), median, first quartile (Q1), third quartile (Q3), minimum, and maximum will be provided.

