## 8.4.2. Secondary Endpoints

Time to resolution of target ulcer(s) up to Week 12: a stratified log-rank test will be used to compare the treatment groups. A Cox regression model will be used to estimate the hazard ratio between voxelotor +SOC and placebo + SOC groups, as appropriate. Time to resolution will be measured (in days) from Day 1 to date of initial closure of the target ulcer. For participants with more than one target ulcer, time to resolution will be based on the time to closure of all target ulcers (ie, initial closure of the last target ulcer to resolve).

Change from baseline in sum of surface area of target ulcer(s) at Week 12: a mixed-effect model for repeated measures will be used to estimate and compare change from baseline in sum of target ulcer(s) surface area between voxelotor + SOC and placebo + SOC groups. The model will include terms for treatment group, study visit, treatment-by-study visit interaction, as well as the stratification factors. Within-participant variability will be modeled using an unstructured covariance matrix.

Incidence of new ulcers by Week 12: the proportion of participants with new ulcer occurrence within 12 weeks of treatment will be compared between treatment groups using a CMH test, stratified by target ulcer size, and target ulcer duration, as appropriate.

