Abbreviations: ALT, alanine aminotransferase; AST, aspartate aminotransferase; BUN, blood urea nitrogen; CGI-C, Clinician Global Impression of Change; EOS, End of study; Hb, hemoglobin; HbS/β0, sickle hemoglobin and one beta thalassemia gene; HbSS, sickle hemoglobin with 2 sickle cell genes; LDH, lactate dehydrogenase; MCH, mean cell hemoglobin; MCHC, mean corpuscular hemoglobin concentration; MCV, mean corpuscular volume; PGI-C, Patient Global Impression of Change; PROMIS, Patient-Reported Outcome Measurements Information System; RBC, red blood cell; RDW, red blood cell distribution width; SOC, standard of care; VAS, visual analog scale; WBC, white blood cell.

- a. Week 28 (Visit 16-B) will be for participants who choose not to enroll or are ineligible for the provision of voxelotor through an alternative source study. At this visit, safety and efficacy assessments will be collected.
- Visits at Weeks 2, 4, 6, 8, and 10.
- Visits at Weeks 14, 16, 18, 20, and 22.
- d. For participants who have completed 12 weeks in the Open-label Treatment Period and continue to receive voxelotor until they have access to voxelotor from an alternative source (eg, through a clinical OLE study sponsored by Pfizer, commercialization of the product, or a managed access program; See Section 5.1). The final study visit for these participants will occur on the day of access to voxelotor from an alternative source.

Period	Screening	Run-in	12-Week Randomized Treatment				label Treat num 12 wo	Follow- up/ EOS Visit a,v	Early Termination Visit	
Visit Number (Week)	Visit 1 (Week -6 to - 2)	Visit 2 (Week -2)	Visit 3 (Week 0)	Visits 4-8 b (Week 2-10)	Visit 9 (Week 12)	Visit 10-14° (Week 14- 22)	Visit 15 (Week 24)	Visit 16-A & onward d (Week 28)	Visit 16-B (Week 28)	
Visit Day	-42 to -14	-14	Day 1	Day 14-70	Day 84	Day 96-154	Day 168	Day 196 & onward	Day 196	
Visit Window	_	+3 days	+1 day	±3 days	±3 days	±3 days	±3 days	±5 days	±7 days	_

- e. This test will be performed at Screening only for the medical diagnosis of SCD, if this diagnosis is not documented in the participant's medical chart.
- f. All Screening evaluations must be completed and reviewed before the Run-in Visit to confirm all eligibility criteria are met. Inclusion and exclusion criteria should be reviewed at Screening, Run-in, and just prior to randomizing each participant to ensure study eligibility is met.

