#### 6.4.1.2. Secondary Endpoint

1. Endpoint: Time (in days) to resolution of target ulcer(s) up to Week 12

Population: ITT population as described in Section 4

Analysis:

A Cox regression model with the treatment group as a covariate will be used to estimate the hazard ratio (voxelotor vs. placebo) and the corresponding two-sided 95% CI by subgroup.

Endpoint: Change from baseline in total surface area of target ulcer(s) at Week 12

Population: ITT population as described in Section 4

Analysis:

MMRM analysis as described in Section 5.2.2.1 will be used and the change from baseline in total surface area of target ulcer(s) at Week 12 as a response variable. The LS means difference (voxelotor vs. placebo) with 95% CI for LS mean difference at Week 12 will be provided by subgroup.

PFIZER CONFIDENTIAL TMF Doc ID: 98.03 Page 28 of 43 Endpoint: Incidence of new ulcers by Week 12

Population: ITT population as described in Section 4

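### Every fallback covariance structure in the MMRM assumes one variance for all visits; if a fallback is used and the spread of ulcer-area change grows toward Week 12, the Week 12 confidence interval is too narrow

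*SAP*

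**What the plan says.** Protocol 8.4.2 names one covariance structure for change in total target-ulcer area and no fallback: "Within-participant variability will be modeled using an unstructured covariance matrix". SAP 5.2.2.1 keeps that choice under REML: the method "will be used with an unstructured covariance matrix to describe the correlation among different visits from the same participant". It then adds the rule "If there are convergence issues with the model, the following structures will be considered in the order listed below until convergence is obtained", followed by spatial power, AR(1) and compound symmetry. Kenward-Roger degrees of freedom apply; no heterogeneous-variance structure and no empirical standard error is named.

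The result reported is for a single visit. SAP 6.2 gives the Week 12 LS mean difference with its 95% CI and p-value. SAP 6.4.1.2 repeats the model in subsets: "The LS means difference (voxelotor vs. placebo) with 95% CI for LS mean difference at Week 12 will be provided by subgroup". SAP 6.4.1 puts these into forest plots and withholds subgroup p-values. Footnote b of the Schedule of Assessments (Protocol Appendix 1) gives "Visits at Weeks 2, 4, 6, 8, and 10", so with Week 12 there are six equally spaced post-baseline visits.

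**The concern.** A model with one common variance bases the Week 12 standard error on variability pooled over Weeks 2 to 12. That is harmless only if the spread of the response is about the same at every visit.

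For change in ulcer area, a growing spread is plausible. At Week 2 most ulcers have had little time to change. By Week 12 a closed ulcer has a change equal to minus its baseline area, while others have barely moved or have grown. Entry requires more than 2 cm² and the visible criteria give no upper limit, so large ulcers that close can contribute large changes. Baseline size enters the main model only as a category, and SAP 6.4.1.2 names no size covariate in the subgroup models.

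If the fallback is used in that situation, the Week 12 interval and p-value claim more precision than the data give. Kenward-Roger does not correct this, because it takes the chosen covariance form as true. With nearly complete data the point estimate barely moves.

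**Working it through.** **Plan's own figures.** Neither document gives an SD of area change at any visit, or a power figure for this endpoint, so there is nothing to reproduce. The stated power of about 90% concerns the primary endpoint. The variance patterns below are assumptions, shown as a range.

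**Step 1: number of parameters.** Six visits (Weeks 2, 4, 6, 8, 10, 12).
- Unstructured: 6 × 7 / 2 = 21.
- Spatial power, AR(1), compound symmetry: 1 variance + 1 correlation = 2 each.
- Heterogeneous AR(1) or heterogeneous compound symmetry: 6 variances + 1 correlation = 7.
- Heterogeneous Toeplitz: 6 variances + 5 correlations = 11.

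**Step 2: spatial power against AR(1).** Spatial power sets the covariance of visits i and j to σ²ρ^|ti − tj|. SAP Appendix 2.1 gives target days 14, 28, 42, 56, 70 and 84, so |ti − tj| = 14|i − j| and the covariance is σ²(ρ^14)^|i − j|. That is AR(1) with correlation ρ^14. Numerically the two matrices agree to rounding error.

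**Step 3: Week 12 standard error under a common variance.** With complete data and a treatment-by-visit mean model, the Week 12 estimate is the difference in Week 12 means. In large samples the model SE divided by the correct SE is

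ratio = √(fitted common variance / true Week 12 variance),

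and a nominal 95% interval covers 2Φ(1.96 × ratio) − 1. For compound symmetry the fitted common variance is the plain average of the six visit variances. Example, SD rising linearly from 1.0 at Week 2 to 2.0 at Week 12: the variances are 1, 1.44, 1.96, 2.56, 3.24 and 4, with sum 14.2 and mean 2.367. The ratio is √(2.367/4) = 0.77 and the coverage 2Φ(1.51) − 1 = 87%.

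For AR(1) (equivalently spatial power) the common variance was found by minimising log|V| + tr(V⁻¹Σ). The assumed correlation between adjacent visits was 0.7 or 0.9.

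| Assumed SD of change, Week 2 to Week 12 | SE ratio, AR(1) and CS | Coverage |
|---|---|---|
| Flat | 1.00 | 95% |
| Rises 1.25-fold | 0.90 | 92% |
| Rises 1.5-fold | 0.84–0.85 | 90% |
| Rises 2-fold | 0.77–0.78 | 87% |
| Rises 3-fold | 0.70–0.73 | 83–85% |
| Rises, then plateau by Week 6 | 0.87–0.92 | 91–93% |
| Proportional to √time | 0.76 | 87% |
| Falls by 20% | 1.13 | 97% |

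**Step 4: simulated trials.** Five ulcer-area scenarios were run, 400 trials each: 40 per arm, 5% monotone dropout, REML, one binary size stratum, and a t quantile on 76 df in place of full Kenward-Roger. Healing rates and measurement error are assumptions. The SD rose toward Week 12 in every scenario.
- AR(1): SE ratio 0.71–0.80, coverage 84–90%.
- Compound symmetry: SE ratio 0.69–0.82, coverage 83–91%.
- Week 12-only analysis with its own variance, same data: coverage 93.5–96.0%.
- In the scenario with no treatment effect, coverage was 84.8% and 83.8%, so the nominal 5% test rejected in 15.2% (AR(1)) and 16.2% (compound symmetry) of trials.

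**The case against.** The strongest reply is that the fallback will seldom be used. Both documents specify an unstructured matrix, and 21 covariance parameters with about 80 participants and six visits will usually converge. The coverage figures are conditional on failure, and nobody can attach a probability to that from the documents. This stands, and it limits the weight of the point.

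A reader might infer that the fallback is likely in the age and country subgroups. The documents do not support that, because they give no subgroup sizes. A small simulation points the other way: with about 8% dropout and 3% missed visits assumed, an unstructured fit reached a usable optimum in 35 of 40 runs at 8 participants, 39 of 40 at 10, 38 of 40 at 12 and 40 of 40 at 16. It used a purpose-written optimiser, so it is only indicative. Without p-values, the subgroup intervals are also descriptive.

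A reader might also infer that the interval is too narrow wherever a fallback is used. That holds only if variance rises over visits. The first modelled response is Week 2, which already contains two weeks of change plus measurement error, so the rise may be modest. Steeper assumptions, such as SD proportional to time (a sixfold rise from Week 2 to Week 12), give coverage near 80%, but nothing in the documents supports them.

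Finally, spatial power and AR(1) coincide exactly only on nominal times. With actual study days inside the ±3-day windows they would differ slightly. The duplication does no harm in itself; it only makes the list shorter than it looks.

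**Conclusion.** The point holds as a conditional one. It is certain from the SAP that all three fallbacks impose equal variance across visits, and that on the nominal schedule the second repeats the first. If the unstructured fit fails and the variance of change rises toward Week 12, the Week 12 SE is understated, illustratively to about 0.7–0.9 of its correct value, with coverage of about 82–92%. These figures rest on assumed variance patterns.

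The exposure is confined to this secondary endpoint's CI and p-value and to any subgroup CI that uses the fallback. The primary exact CMH test is untouched. PROMIS and VAS have one post-baseline assessment by Week 12 and are little affected. It is a cheap improvement to a contingency rule and does not undermine the main analysis.

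**What to change.** In SAP 5.2.2.1, replace the fallback list with heterogeneous Toeplitz, then heterogeneous AR(1), then heterogeneous compound symmetry, keeping Kenward-Roger, and drop the duplicate structure. Allow a homogeneous structure only as a last resort, and then with a small-sample-corrected empirical standard error in place of Kenward-Roger. An uncorrected sandwich estimator is not a good general substitute: it tends to be too small in small samples and is not normally combined with Kenward-Roger.

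The cost is one line of text and a few more variance parameters: 7 for heterogeneous AR(1) or heterogeneous compound symmetry, and 11 for heterogeneous Toeplitz, against 2 now and 21 for unstructured. Heterogeneous Toeplitz may itself fail in a very small subgroup, which is why the two 7-parameter structures follow it.
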